15.5 Enrollment/Stratification/Randomization/Blinding Procedures

This study uses a "precision" clinical trial framework that leverages prior information to target treatment adherence support to individuals based upon their characteristics (i.e., propensity for nonadherence) while preserving ability to assess the average treatment effect and differences by arms within groups defined by these characteristics (**Figure 15.5**). Specifically, an individual,

unblinded, unbalanced, blocked allocation approach based on prior information of the patient's propensity for failure will be used.

Data on early ART refills/HIV viral suppression (3-6 months after ART initiation) from existing ICCs will be used to develop an algorithm to predict propensity for HCV treatment failure. We are currently unaware of any large databases that contain information on SVR among active PWID in India that we could use and therefore, opted to use early ART refills/viral suppression among HIV-positive persons as a surrogate. The time frame being used is comparable to a full course of HCV treatment. We will develop the score using an approach that incorporates an internal-external cross validation

procedure⁹⁶ where the unit for splitting data will be study site. Each site will be left out once with validation conducted on the remaining pooled set of data. The final model is based on the pooled dataset which can be considered to be an externally validated model. This assures that the final model is based on the pooled data thus maximizing sample size while at the same time tempering overoptimistic model performance in an independent set of data.

In a preliminary analysis, among 119 clients newly initiating ART, we developed a model that had high predictive accuracy (area under the receiver operating characteristics curve=0.81) for early adherence. Importantly all of the factors included in this model (age, employment, injection frequency, OAT use, living with spouse/family, having told someone about their HIV status and readiness for treatment) are either routinely captured in the ICC or can be added to a brief intake survey. We will modify this algorithm based on an expanded analysis that includes ~500 persons initiating ART. We anticipate splitting at the median of the score but this will be reassessed once the model is complete. Distributions of the score within independent samples of the population will be assessed prior to implementation.

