At the Entry visit, prior to randomization and treatment initiation, each participant will undergo a short survey to capture information on barriers/facilitators to treatment adherence identified in the prediction model. Responses to this survey will be captured in an eCRF and integrated with other data from the EHR. The algorithm will be used to classify persons into two strata according to their propensity for HCV treatment failure (minimal or elevated risk).

Individuals will be preferentially randomized to the support level that matches their failure risk. Those at elevated risk for treatment failure will be randomized at an allocation ratio of 3:2:1 for high, medium and low intensity support respectively. Those at minimal risk will be randomized at a ratio of 1:2:3 to high, medium and low-intensity support, respectively.

Randomization will be integrated into the EHR. The Study Nurse who will complete the survey will receive the determination of study arm from an automated program. Both study staff and study participants will be blinded to the designation of minimal/elevated risk stratum.

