Effect of delays in treatment completion on SVR. Additional exploratory analyses will evaluate the impact of non-adherence and delays in completing treatment on SVR. Initial analyses will incorporate data from all three arms. Two variables will be calculated: 1) the percentage of doses completed (as described above); and 2) days to treatment completion. While the scheduled course of treatment will be 84 days for most, participants will be instructed to take all of the doses prescribed (even if doses are missed and the total time for treatment completion extends beyond 84 days. In separate models, log-binomial regression will be used to estimate the association between 1) estimated adherence; and 2) days to treatment completion and SVR. These analyses will be combined across risk strata and treatment arm but these variables will be included as covariates. Additional analysis will be conducted exclusively among participants assigned to Arm 3 (high intensity support) where adherence data will be objectively collected using biometric data.

Estimation of heterogeneity in treatment effect and estimation of average treatment effect.

Additional analyses will be completed to estimate heterogeneity in treatment effect and the average treatment effect for the primary (SVR) and secondary outcomes (treatment completion) defined above.

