The average treatment effect will be determined in order to estimate the effect of the different support strategies in the overall population. Under the unbalanced randomization scenario that is planned, a prognostic score is intentionally created. This score lies between the causal pathway from the individual characteristics to the treatment assignment, thus introducing an "informed confounding", i.e., the causal relationship between treatment assignment and outcome is confounded by the prognostic score (i.e., individual's propensity for treatment failure). To estimate the unbiased, average treatment effect, given that there is information on how the prognostic score affects study arm allocation, the targeted randomization can be used to reweight the sample back to the initial sample as if the randomization allocation was equivalent to all levels of the prognostic score. That is, by using inverse probability of treatment weights, the relationship between the prognostic score and treatment assignment is removed to estimate the average treatment effect to provide answers about whether the high and moderate intensity interventions resulted in superior outcomes in the overall population (i.e., is high intensity support a superior intervention to standard of care in all PWID regardless of propensity for treatment failure?).

These analyses will seek to use information from the prognostic score and the observed data to identify the optimal threshold for assigning treatment support. That is, by assessing heterogeneity in treatment effect by level of prognostic score, we will potentially be able to identify a range of scores to assist in the decision of whether low, moderate, or high level of support would be most efficacious for individuals based upon the characteristics that determine their prognostic score. First, within the two strata defined by the prognostic score, there remains variability in the prognostic score. Therefore, we will evaluate the impact of the interaction between the prognostic score and the intensity of support received (low, medium and high intensity) on SVR and treatment completion rates in the full sample. The goal of this analysis will be to evaluate the heterogeneity of treatment effect within strata.

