Of additional interest is identifying the heterogeneous treatment effect of the intensity of support received on SVR and secondary outcomes across the *entire distribution of* prognostic score (note that the prognostic score will be continuous). Therefore, by using the weighted (by inverse probability of treatment weights) study sample, the interaction between the prognostic score and intensity of support received on SVR and treatment completion rates can be examined across the entire study population. Specifically, a model will include the indicator variables for level of support, the main effect of the prognostic score, and the interaction term. The model will allow for non-linear relationship between prognostic score and outcomes and depict the estimated treatment effect graphically to determine the optimal cut-points of the prognostic score to assign low, medium and high intensity treatment support to maximize SVR.

Effect of heterogeneity of intervention effect by gender. It is of interest to examine whether the impact of the intervention varies by gender. We anticipate that power will be limited in these analyses since in many of the field sites, the number of women is negligible, consistent with the epidemiology of injection drug use in India. However, we will conduct stratified analyses to explore whether the effect of the level of treatment support varies by gender within strata of treatment nonadherence risk. We will also conduct the analyses of the average treatment effect stratified by gender.

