Annual assessments of HIV viral load among HIV/HCV coinfected participants in the 7 ICCs are expected as part of other ICC activities and standard of care at Indian government ART centers. All available viral load measurements for HIV/HCV co-infected PWID enrolled in the trial will be used. Viral suppression will be defined as HIV RNA less than LLOQ. We will compare viral suppression across two groups defined by primary outcome status, which will be cured vs. not cured using logistic regression with generalized estimating equations (GEE) to account for repeated measures within individuals. Because these groups will be defined by the primary outcome and no longer balanced by randomization, analysis will be adjusted for confounding factors including demographics, substance use, needle sharing, MOUD, SSP use, social support and frequency of visits to the ICC. Analyses will be combined across all groups but we will include a covariate for the classification of risk of treatment failure (minimal or elevated) and intervention received. In order to account for missing data due to loss-to-follow-up, we will use inverse-weighting methods.^{4,5}

2d.1. Sensitivity analyses. We will vary the threshold for HIV viral suppression (<150 copies/ml vs. 400 copies/ml vs. 1000 copies/ml) and will also incorporate the revised definition of SVR vs. treatment failure using sequence data.

3. Exploratory analysis

3a. Impact of interventions on medication for opioid use disorder (MOUD) utilization. Daily MOUD utilization data is available in the electronic health record. We will explore the impact of the interventions within strata by arm on new MOUD initiation and MOUD retention using methods of survival analysis, logistic regression with GEE and growth mixture models. Analyses will be adjusted for site. Additional sensitivity analyses will be similar to those reported in the primary and secondary outcome analyses and will include accounting for the prognostic score.

3b. Impact of interventions on quality of life.

Quality of life data is captured at the SVR visit and at semi-annual post-treatment follow-up visits. Using logistic and linear regression with GEE, we will explore the impact of interventions within strata on quality of life after treatment.

3c. Impact of interventions on mortality.

Using Poisson regression, we will explore the impact of interventions within strata on all-cause mortality.

3d. Effect of delays in treatment completion on SVR.

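### The exploratory adherence and delay models for SVR adjust only for the two-level risk stratum and arm, leaving out the continuous prognostic score and site that the plan already records

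*Protocol*

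**What the plan says.** The aim in Protocol 15.7.2.3, repeated in SAP 3d, is causal in wording: "Additional exploratory analyses will evaluate the impact of non-adherence and delays in completing treatment on SVR". Data from all three arms are pooled. SVR is regressed on the percentage of doses completed and, in a separate model, on days to completion. On covariates, both documents say: "These analyses will be combined across risk strata and treatment arm but these variables will be included as covariates". Neither names site, the continuous score or any baseline factor for these models. The additional analysis within Arm 3 names no covariates at all.

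Elsewhere the plan says the following about the omitted variables.

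- The stratum is a two-level classification, but the same protocol section states "note that the prognostic score will be continuous" and that "within the two strata defined by the prognostic score, there remains variability in the prognostic score".
- Protocol 15.5 lists the preliminary score inputs as "age, employment, injection frequency, OAT use, living with spouse/family, having told someone about their HIV status and readiness for treatment". Their discrimination for early adherence to antiretroviral therapy in 119 clients is given as "area under the receiver operating characteristics curve=0.81".
- Protocol 7.2.3 says that the score rests on factors that influence the outcome.
- Site is a fixed effect in the primary SVR model (SAP 1). The score is a covariate in sensitivity analyses of the arm comparisons (SAP 1b, 2a.1, 2b.2). SAP 3a adjusts for site and accounts for the score, and SAP 3e models the score non-linearly.
- For HIV suppression by cure status, SAP 2d says: "Because these groups will be defined by the primary outcome and no longer balanced by randomization, analysis will be adjusted for confounding factors".

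**The concern.** Doses taken and time to completion are participant behaviour, so randomization does not balance them. The score was built to predict adherence, and a median split removes only part of its relation to adherence. If the score also bears on SVR by a route other than doses taken, what remains inside each stratum confounds the estimate.

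The documents supply one such route. Injection frequency and OAT use are score inputs, the protocol hypothesizes that OAT engagement lowers reinfection (7.3, hypothesis 4), and the SVR sample may be taken up to 60 weeks after treatment. Reinfection before that sample counts as failure, apart from an exploratory reclassification by sequencing in SAP 1e that is specified for the analyses by arm. Site can act in the same way if centres differ in both adherence and SVR.

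At stake is the reading of how much missed dosing or delay SVR can tolerate. The present model could overstate that penalty.

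**Working it through.** The documents give no effect size, power or score–SVR association for this analysis, so there is no stated figure to reproduce. The check asks what the named model returns when adherence has no effect on SVR.

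**Inputs from the documents.** N = 3,000; 7 sites; median split of the score; allocation 3:2:1 (high:medium:low) at elevated risk and 1:2:3 at minimal risk; SVR 85% as the illustrative level (Protocol 15.4); adherence cut at 90% of doses (15.7.2.2); Poisson regression with robust variance.

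**Assumptions, not in the documents.** Score S is standard normal. Logit of non-adherence = −1.0 + d·S − 0.3·arm (0, 1, 2) + site effect. Logit of failure = ln(0.15/0.85) + ln(OR)·S + site effect, with no adherence or arm term. Site effects have the stated SD and are the same in both equations, which is the least favourable case. The slope is d = √2·Φ⁻¹(AUROC): √2 × 0.385 = 0.545 for a target of 0.65, and √2 × 0.878 = 1.242 for 0.81. Re-running this set-up without site effects gives realised AUROCs of about 0.62 and 0.76, and 23% to 26% non-adherent, so the rows below are somewhat milder than their targets suggest.

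**Hand check at d = 1.242, OR 1.5.** SVR is about 80.1% at elevated and 88.5% at minimal risk. Within strata, non-adherent participants score higher by 1.04 − 0.63 = 0.41 SD (elevated) and −0.51 − (−0.84) = 0.33 SD (minimal). With p the SVR, the false ratio (non-adherent to adherent) is about RR = 1 − (1 − p)·ln(OR)·Δ:

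- elevated: 1 − 0.199 × 0.405 × 0.41 = 0.967
- minimal: 1 − 0.115 × 0.405 × 0.33 = 0.985

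The simulated pooled value, 0.972, lies between them.

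**Simulation, 500 replicates per row, true RR = 1.** Each cell gives the RR and the share of trials with p < 0.05.

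| Target AUROC | OR of failure per SD | Site SD | Stratum + arm | Plus score, score², site |
|---|---|---|---|---|
| 0.81 | 1.0 | 0 | 1.000, 3% | 1.000, 3% |
| 0.65 | 1.25 | 0 | 0.992, 8% | 0.998, 6% |
| 0.65 | 1.5 | 0 | 0.986, 9% | 1.000, 5% |
| 0.81 | 1.25 | 0 | 0.984, 12% | 0.999, 6% |
| 0.81 | 1.5 | 0 | 0.972, 29% | 1.000, 4% |
| 0.81 | 2.0 | 0 | 0.946, 72% | 1.001, 4% |
| none | 1.0 | 0.3 | 0.988, 11% | 1.000, 5% |
| none | 1.0 | 0.5 | 0.968, 35% | 1.001, 4% |
| 0.65 | 1.5 | 0.3 | 0.975, 24% | 0.999, 4% |
| 0.81 | 1.5 | 0.3 | 0.960, 53% | 0.998, 4% |

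The Monte Carlo standard error at 5% is √(0.05 × 0.95/500) = 1.0 percentage point, so the 3% to 6% values are compatible with nominal.

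**Planned exposure.** A separate simulation used percentage of doses instead of the 90% cut. The stratum-and-arm model rejected in 7% to 9% of trials with no score or site link, 13% to 19% at OR 1.25, and 20% to 97% at OR 1.5 to 2. With score and site added, the rate was about 3% to 9%. Days to completion was not simulated.

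**Limit of the remedy.** Adding an unmeasured common cause (0.5 logit per SD in both equations) to the last row of the table gives RR 0.923 and 96% rejection under the present model, against 0.956 and 48% after adjustment.

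**The case against.** The strongest reply is that this is an exploratory analysis whose models are said to estimate an association; no hypothesis, endpoint or power statement depends on it. The covariate sentence explains how pooling is handled and does not exclude other covariates, whereas the adherence section of Protocol 15.7.2.2 does say that adjustment is for site alone. This stands as regards weight. It does not remove the point, because a pre-specified model is read from the covariates it names.

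The size also depends on an assumed score–SVR link that bypasses adherence. In a re-run at OR 1.1 to 1.25, the false RR (adherent to non-adherent) was only 1.01 to 1.02, significant in 3% to 11% of trials. If the score acts on SVR solely through adherence, with a real effect of 1.0 logit, the two models agree (1.196 against 1.196). Both results stand: the bias is conditional.

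SAP 2d is an imperfect precedent. It adjusts for the binary risk class and behavioural factors, but not for the continuous score or site. It supports the principle of adjusting non-randomized comparisons, not this exact list.

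A route through attendance at the SVR visit would need untested participants to count as failures here, which SAP 3d does not say. The reinfection route does not need that.

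**Conclusion.** The point holds as a minor one. Two non-randomized exposures are analysed with only a coarse version of the available score and without site, so an association can appear when missed doses have no effect. The false-positive rate ranges from near nominal to very high. Where it falls depends on how strongly score and site relate to SVR outside dosing and how well the score predicts non-adherence, and the documents settle neither.

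A reader might infer more than this, and the documents do not support it:

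- That a spurious result is to be expected. With no score or site link there is no material inflation.
- That 0.81 describes prediction of missed HCV doses. It is a preliminary figure for early antiretroviral adherence in 119 clients, and the model is to be revised on about 500.
- That a false RR of a few percent can be set against the detectable RRs in Table 15.4.1. Those are arm contrasts within a stratum, not a pooled adherence contrast.
- That programs would over-invest in support. Decisions on support rest on the randomized comparisons, which this analysis does not touch.
- That adjustment removes the confounding. It removes the part carried by score and site. The simulated return to nominal follows largely from those being the only confounders simulated.

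**What to change.** In SAP 3d and Protocol 15.7.2.3, add the continuous prognostic score with a non-linear term (as in SAP 3e) and site as a fixed effect, alongside stratum and arm, in both the adherence and the delay model. Report the stratum-and-arm-only model as secondary. Describe the result as an association, and state that confounding by unmeasured or on-treatment factors may remain. HIV status, cirrhosis status and regimen are optional additions; no calculation here shows that they are needed.

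The cost is wording. The score is produced at entry, before treatment, and site is recorded. One linear and one squared score term plus 6 site indicators make 8 extra parameters, a negligible loss of precision with about 3,000 participants.

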16. DATA HANDLING AND RECORDKEEPING

16.1 Data Management Responsibilities

This study will be 7 field sites throughout India but will be coordinated by a single site, YRG CARE) in Chennai, Tamil Nadu, India with oversight from investigators at the Johns Hopkins Bloomberg School of Public Health and the Johns Hopkins School of Medicine. Investigators from Johns Hopkins and YRGCARE will oversee all aspects of the trial including participant recruitment, data collection, laboratory testing, biological sample storage, and data management. Additional details can be found in the **Data and Safety Monitoring Plan**.

16.2 Source Documents and Access to Source Data/ Documents

Source documents for this study are the eCRFs and the EHR which will be made available to the sites for data entry. The eCRFs and the EHR will be hosted online and copies will also be available on the laptop (in case of regions where the internet connectivity is limited). Additional details can be found in the **Data Safety and Monitoring Plan.**

16.3 Quality Control and Quality Assurance

16.3.1. Procedures to ensure the validity and integrity of the data

All field staff, interviewers, phlebotomists and clinicians who will come into contact with study participants will be required to complete research ethics and good clinical practice (GCP) training.

Lab technicians/phlebotomists at YRG CARE have undergone training on research ethics and good clinical laboratory practices (GCLP). The YRG CARE Infectious Disease Lab is certified by the College of American Pathologists, United Kingdom National External Quality Assurance Scheme, and the Virologic Quality Assessment Program, US and by the AIDS Clinical Trials Group and Abbott Laboratories Inc, US to perform HIV-1 genotypic resistance testing. GCLP are monitored by Johns Hopkins, Family Health International, and PPD.

Additional details can be found in the **Data Safety and Monitoring Plan**. Internal and external study monitors will implement routine quality management activities detailed in the **Study MOP**.

16.3.2. Procedures to guarantee the accuracy and completeness of the data

Our primary mode of data collection will be through the EHR at the ICCs and study specific eCRFs. Additional details can be found in the **Data Safety and Monitoring Plan**.

17. CLINICAL SITE MONITORING

Clinical site monitoring will include both internal and external monitoring.

17.1 Internal Site Monitoring

Internal monitoring will include annual site visits will be made by the PIs as well as quarterly visits from three monitors employed by YRGCARE. Details of these monitoring activities can be found in the **Data and Safety Monitoring Plan**.

17.2 External Site Monitoring

An independent monitor contracted by YRGCARE will conduct external monitoring assessments. Over the course of the trial, there will be three on-site monitoring visits and three remote monitoring visits for a total of two monitoring visits per year per site. Additional details can be found in the **Data and Safety Monitoring Plan**.

18. HUMAN SUBJECTS PROTECTIONS

18.1 Institutional Review Board/Ethics Committee

The protocol and all informed consent documents will be approved by the Institutional Review Boards of the Johns Hopkins School of Medicine in the US and the YRGCARE in Chennai, India. In addition, the study will be approved by the Indian Council of Medical Research and the Health Ministry Screening Committee. Any subsequent modifications will be reviewed and approved by both the Johns Hopkins and the YRGCARE IRBs. IRB continuing review and approval will be obtained from both the Johns Hopkins and YRGCARE IRBs once a year. If IRB approval expires or lapses, all ongoing research activities will stop unless the PIs determine that it is the best interests of already enrolled participants to continue their study-related activities. New participants will not be enrolled in the study until the IRB approval to continue the research is obtained.

